## Insomnia Severity Index

The Insomnia Severity Index has seven questions. The seven answers are added up to get a total score. When you have your total score, look at the 'Guidelines for Scoring/Interpretation' below to see where your sleep difficulty fits.

For each question, please ~~CIRCLE~~ (SAY WHICH choice) ~~number~~ that best describes your answer.

*Please rate the CURRENT (i.e., LAST 2 WEEKS) SEVERITY of your insomnia problem(s).*

Insomnia Problem	None	Mild	Moderate	Severe	Very Severe
1. Difficulty Falling Asleep	0	1	2	3	4
2. Difficulty Staying Asleep	0	1	2	3	4
3. Problems Waking up too early	0	1	2	3	4

4. How SATISFIED/DISSATISFIED are you with your CURRENT sleep pattern?

Very Satisfied      Satisfied      Moderately Satisfied      Dissatisfied      Very Dissatisfied  
0                    1                    2                    3                    4

5. How NOTICEABLE to others do you think your sleep problem is in terms of impairing the quality of your life?

Not at all Noticeable      A Little      Somewhat      Much      Very Much Noticeable  
0                    1                    2                    3                    4

6. How WORRIED/DISTRESSED are you about your current sleep problem?

Not at all Worried      A Little      Somewhat      Much      Very Much Worried  
0                            1                            2                            3                            4

7. To what extent do you consider your sleep problem to INTERFERE with your daily functioning (e.g. daytime fatigue, mood, ability to function at work/daily chores, concentration, memory, etc.) CURRENTLY?

Not at all Interfering      A Little      Somewhat      Much      Very Much Interfering  
0                            1                            2                            3                            4

**Guidelines for Scoring/Interpretation:**

Add the scores for all seven items (questions 1 + 2 + 3 + 4 + 5 + 6 + 7) = \_\_\_\_\_ your total score

Total score categories:

0–7 = No clinically significant insomnia

8–14 = Subthreshold insomnia

15–21 = Clinical insomnia (moderate severity) 22–28 = Clinical insomnia (severe)

**Informed Consent Review** [either continuation of above telephone conversation or in later call]

Note: the Informed Consent does not have to be read word-for-word over the telephone but major points need to be reviewed, including:

- Subject Bill of Rights
- Background and Purpose
- Study Procedures/Plan
- Responsibilities
- Potential Benefits
- Confidentiality
- Participation is Voluntary
- Medical Treatment and Compensation
- Significant New Information
- Time Requirements
- Possible Risks and Discomforts
- Alternatives to Participate
- Costs and payments
- Right of Investigator to Withdraw Subjects

Persons to Contact if Questions:

Contact Information: [name] at [contact]

For questions about your rights as a research participant, you can call the UCSF Institutional Review Board at [contact].

- Would you be interested in being screened to see if you're eligible for this research? It will take about 30 minutes to go over these questions.
- It's fine if you want to get back to us later about scheduling a telephone screening appointment.  [If potential subject wants to schedule phone appointment] When would be a good day and time?

## Epworth Sleepiness Scale

Name: \_\_\_\_\_ Today's date: \_\_\_\_\_

Your age (Yrs): \_\_\_\_\_

Your sex (Male = M, Female = F): \_\_\_\_\_

How likely are you to doze off or fall asleep in the following situations, in contrast to feeling just tired?

This refers to your usual way of life in recent times.

Even if you haven't done some of these things recently try to work out how they would have affected you.

Use the following scale to choose the **most appropriate number** for each situation:

- 0 = would **never** doze
- 1 = **slight chance** of dozing
- 2 = **moderate chance** of dozing
- 3 = **high chance** of dozing

*It is important that you answer each question as best you can.*

Situation	Chance of Dozing (0-3)
Sitting and reading	
Watching TV	
Sitting, inactive in a public place (e.g. a theatre or a meeting)	
As a passenger in a car for an hour without a break	
Lying down to rest in the afternoon when circumstances permit	
Sitting and talking to someone	
Sitting quietly after a lunch without alcohol	
In a car, while stopped for a few minutes in the traffic	

**THANK YOU FOR YOUR COOPERATION**

© M.W. Johns 1990-97

## Medical Outcomes Study Questionnaire Short Form 36 Health Survey

This survey asks for your views about your health. This information will help keep track of how you feel and how well you are able to do your usual activities. Thank you for completing this survey! For each of the following questions, please (say which choice) circle the number that best describes your answer.

1. In general, would you say your health is:	
Excellent	1
Very good	2
Good	3
Fair	4
Poor	5
2. Compared to one year ago,	
Much better now than one year ago	1
Somewhat better now than one year ago	2
About the same	3
Somewhat worse now than one year ago	4
Much worse now than one year ago	5

3. The following items are about activities you might do during a typical day. Does your health now limit you in these activities? If so, how much?

**(Circle One Number on Each Line)**

	Yes, Limited a Lot (1)	Yes, Limited a Little (2)	No, Not limited at All (3)
a. Vigorous activities , such as running, lifting heavy objects, participating in strenuous sports	1	2	3
b. Moderate activities , such as moving a table, pushing a vacuum cleaner, bowling, or playing golf	1	2	3
c. Lifting or carrying groceries	1	2	3
d. Climbing several flights of stairs	1	2	3
e. Climbing one flight of stairs	1	2	3

f. Bending, kneeling, or stooping	1	2	3
-----------------------------------	---	---	---

g. Walking more than a mile	1	2	3
h. Walking several blocks	1	2	3
i. Walking one block	1	2	3
j. Bathing or dressing yourself	1	2	3

4. During the **past 4 weeks**, have you had any of the following problems with your work or other regular daily activities **as a result of your physical health?**

**(Circle One Number on Each Line)**

	Yes (1)	No (2)
a. Cut down the amount of time you spent on work or other activities	1	2
b. Accomplished less than you would like	1	2
c. Were limited in the kind of work or other activities	1	2
d. Had difficulty performing the work or other activities (for example, it took extra effort)	1	2

5. During the **past 4 weeks**, have you had any of the following problems with your work or other regular daily activities **as a result of any emotional problems** (such as feeling depressed or anxious)?

**(Circle One Number on Each Line)**

	Yes	No
a. Cut down the amount of time you spent on work or other activities	1	2
b. Accomplished less than you would like	1	2
c. Didn't do work or other activities as carefully as usual	1	2

6. During the past 4 weeks, to what extent has your physical health or emotional problems interfered with your normal social activities with family, friends, neighbors, or groups?	
Not at all	1
Slightly	2
Moderately	3
Quite a bit	4
Extremely	5

7. How much bodily pain have you had during the past 4 weeks?	
None	1
Very mild	2
Mild	3
Moderate	4
Severe	5
Very severe	6
8. During the past 4 weeks, how much did pain interfere with your normal work (including both work outside the home and housework)?	
Not at all	1
A little bit	2
Moderately	3
Quite a bit	4
Extremely	5

These questions are about how you feel and how things have been with you **during the past 4 weeks**. For each question, please give the one answer that comes closest to the way you have been feeling. **(Circle One Number on Each Line)**

9. How much of the time during the **past 4 weeks** . . .

	All of the Time	Most of the Time	A Good Bit of the Time	Some of the Time	A Little of the Time	None of the Time
a. Did you feel full of pep?	1	2	3	4	5	6
b. Have you been a very nervous person?	1	2	3	4	5	6
c. Have you felt so down in the dumps that nothing could cheer you up?	1	2	3	4	5	6
d. Have you felt calm and peaceful?	1	2	3	4	5	6
e. Did you have a lot of energy?	1	2	3	4	5	6

	All of the Time	Most of the Time	A Good Bit of the Time	Some of the Time	A Little of the Time	None of the Time
f. Have you felt downhearted and blue?	1	2	3	4	5	6
g. Did you feel worn out?	1	2	3	4	5	6
h. Have you been a happy person?	1	2	3	4	5	6
i. Did you feel tired?	1	2	3	4	5	6

10. During the past 4 weeks, how much of the time has your physical health or emotional problems interfered with your social activities (like visiting with friends, relatives, etc.)? (Circle One Number)	
All of the time	1
Most of the time	2
Some of the time	3
A little of the time	4
None of the time	5

**11. How TRUE or FALSE is each of the following statements for you.(Circle One Number on Each Line)**

	Definitely True	Mostly True	Don't Know	Mostly False	Definitely False
a. I seem to get sick a little easier than other people	1	2	3	4	5
b. I am as healthy as anybody I know	1	2	3	4	5
c. I expect my health to get worse	1	2	3	4	5
d. My health is excellent	1	2	3	4	5

## QUICK DEMENTIA RATING SYSTEM (QDRS)

These next questions are somewhat personal and will help us understand the severity of your symptoms. Please find a private space.

The following descriptions characterize changes in cognitive and functional abilities. Please compare yourself now to how you used to be—the key feature is change. Choose one answer for each category that best fits you. (Note – not all descriptions need to be present to choose an answer.) (for each category there are 5 levels of severity of change)

Which category best describes your:

1. Memory and recall	
No obvious memory loss or inconsistent forgetfulness that does not interfere with function in everyday activities	0
Consistent mild forgetfulness or partial recollection of events that may interfere with performing everyday activities; repeats questions/statements, misplaces items, forgets appointments	0.5
Mild to moderate memory loss; more noticeable for recent events; interferes with performing everyday activities	1
Moderate to severe memory loss; only highly learned information remembered; new information rapidly forgotten	2
Severe memory loss, almost impossible to recall new information; long-term memory may be affected	3
2. Orientation	
Fully oriented to person, place, and time nearly all the time	0
Slight difficulty in keeping track of time; may forget day or date more frequently than in the past	0.5
Mild to moderate difficulty in keeping track of time and sequence of events; forgets month or year; oriented to familiar places but gets confused outside familiar areas; gets lost or wanders	1
Moderate to severe difficulty, usually disoriented to time and place (familiar and unfamiliar); frequently dwells in past	2
Only oriented to their name, although may recognize family members	3
3. Decision-making and problem-solving abilities	
Solves everyday problems without difficulty; handles personal business and financial matters well; decision-making abilities consistent with past performance	0
Slight impairment or takes longer to solve problems; trouble with abstract concepts; decisions still sound	0.5
Moderate difficulty with handling problems and making decisions; defers many decisions to others; social judgment and behavior may be slightly impaired; loss of insight	1
Severely impaired in handling problems, making only simple personal decisions; social judgment and behavior often impaired; lacks insight	2
Unable to make decisions or solve problems; others make nearly all decisions for patient	3
4. Activities outside the home	
Independent in function at the usual level of performance in profession, shopping, community and religious activities, volunteering, or social groups	0
Slight impairment in these activities compared with previous performance; slight change in driving skills; still able to handle emergency situations	0.5
Unable to function independently but still may attend and be engaged; appears "normal" to others; notable changes in driving skills; concern about ability to handle emergency situations	1
No pretense of independent function outside the home; appears well enough to be taken to activities outside the family home but generally needs to be accompanied	2
No independent function or activities; appear too ill to be taken to activities outside the home	3

5. Function at home and hobby activities	
Chores at home, hobbies and personal interests are well maintained compared with past performance	0
Slight impairment or less interest in these activities; trouble operating appliances (particularly new purchases)	0.5
Mild but definite impairment in home and hobby function; more difficult chores or tasks abandoned; more complicated hobbies and interests given up	1
Only simple chores preserved, very restricted interest in hobbies which are poorly maintained	2
No meaningful function in household chores or with prior hobbies	3
6. Toileting and personal hygiene	
Fully capable of self-care (dressing, grooming, washing, bathing, toileting)	0
Slight changes in abilities and attention to these activities	0.5
Needs prompting to complete these activities but may still complete independently	1
Requires some assistance in dressing, hygiene, keeping of personal items; occasionally incontinent	2
Requires significant help with personal care and hygiene; frequent incontinence	3
7. Behavior and personality changes	
Socially appropriate behavior in public and private; no changes in personality	0
Questionable or very mild changes in behavior, personality, emotional control, appropriateness of choices	0.5
Mild changes in behavior or personality	1
Moderate behavior or personality changes, affects interactions with others; may be avoided by friends, neighbors, or distant relatives	2
Severe behavior or personality changes; making interactions with others often unpleasant or avoided	3
8. Language and communication abilities	
No language difficulty or occasional word searching; reads and writes as in the past	0
Consistent mild word finding difficulties, using descriptive terms or takes longer to get point across, mild problems with comprehension, decreased conversation; may affect reading and writing	0.5
Moderate word finding difficulty in speech, cannot name objects, marked reduction in work production; reduced comprehension, conversation, writing, and/or reading	1
Moderate to severe impairments in speech production or comprehension; has difficulty in communicating thoughts to others; limited ability to read or write	2
Severe deficits in language and communication; little to no understandable speech is produced	3
9. Mood	
No changes in mood, interest, or motivation level	0
Occasional sadness, depression, anxiety, nervousness, or loss of interest/motivation	0.5
Daily mild issues with sadness, depression, anxiety, nervousness, or loss of interest/motivation	1
Moderate issues with sadness, depression, anxiety, nervousness, or loss of interest/motivation	2
Severe issues with sadness, depression, anxiety, nervousness, or loss of interest/motivation	3
10. Attention and concentration	
Normal attention, concentration, and interaction with his or her environment and surroundings	0
Mild problems with attention, concentration, and interaction with environment and surroundings, may appear drowsy during day	0.5
Moderate problems with attention and concentration, may have staring spells or spend time with eyes closed, increased daytime sleepiness	1
Significant portion of the day is spent sleeping, not paying attention to environment, when having a conversation may say things that are illogical or not consistent with topic	2
Limited to no ability to pay attention to external environment or surroundings	3

Total QDRS score: \_\_\_\_\_

- 0 to 1.5 = CDR 0 (normal)

- $2.0 \text{ to } 6.0 = \text{CDR 0.5 (MCI) -- Eligible}$
- $6.5 \text{ to } 12.5 = \text{CDR 1 (mild) -- Eligible}$
- $13.0 \text{ to } 17.5 = \text{CDR 2 (moderate)}$
- $\geq 18.0 = \text{CDR 3 (severe)}$

*If the QDRS score is 6.5 to 12.5, they are eligible. Otherwise:  }*

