***Full Study Title: Napping, Sleep, Cognitive Decline and Risk of Alzheimer's Disease***

Principal Investigator: [name]

University of California, San Francisco  
[name]  
[name]  
[contact]

Sponsor

National Institutes of Health

Title	Napping, Sleep, Cognitive Decline and Risk of Alzheimer's Disease (SleepTIGHT)
Study Duration	Trial duration: 9 weeks + follow-up after 24 weeks
Study Center	UCSF Psychiatry department
Objective	Determine feasibility of online CBT-I in an older adult population (age 65+)
Number of Subjects	40

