Diagnosis and Main Inclusion Criteria	
Inclusion Criteria
 
 
• 1) Age 65+,
 
• 2) evidence of MCI, defined as: self-reported quick dementia rating system (QDRS) - derived global clinical dementia rating score of .5,
 
• 3) adequate visual and auditory acuity to allow neuropsychological testing;
 
• 4) evidence of subthreshold or clinical insomnia, defined as a score of 8 or more on the insomnia severity index,
 
• 5) ability to speak understand and write in English, 6) study partner willing to participate,
 
• 7) capacity to give written informed consent; and
 
• 8) owns one or more smartphone or tablet devices that can be used to access the internet and to participate in video conferences.
 
 
Exclusion Criteria
 
 
• 1) Self-reported diagnosis by a physician of any major neurologic disease such as Alzheimer's disease, other dementia, Parkinson's disease, multiple sclerosis, epilepsy, Huntington's disease;
 
• 2) History of brain tumor or significant head trauma (loss of consciousness >30 minutes);
 
• 3) Evidence (CT or MRI scans within 12 months prior to screening) of brain infarction or other focal lesions; 4) Any comorbid psychiatric conditions or severe personality disorder within the past 2 years (by DSM-V), such as major depression, bipolar disorder, schizophrenia, and other psychotic features;
 
• 5) Any uncontrolled medical conditions or systemic illness that might lead to difficulty complying with the study protocol;
 
• 6) Any concomitant treatment that might confound the results (participants must be off all psychotropic medications, including hypnotic medications, and non-pharmacological treatments, for at least 30 days prior to screening);
 
• 7) History of alcohol or substance abuse within the past 2 years;
 
• 8) Shift workers; and
 
• 9) Any inadequately treated primary or secondary sleep disorders
 

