### Purpose

In order to address the hypothesis that CBT-I is feasible in patients with MCI, and could potentially improve their sleep quality, slow down cognitive decline, and improve quality of life of patients and caregivers, we will use a parallel-designed randomized controlled trial to pilot test the feasibility and effects of a digital CBT-I treatment program in those with MCI.

This study focuses on testing the validity of this CBT-I program while exploring its preliminary effects on sleep/cognition.

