## APPENDIX B.

### SleepTIGHT phone screening script

#### INTERVIEWER INSTRUCTIONS

Read **bolded** text verbatim. Answer any questions as needed. Record all contacts in the contact log.

If a  is reached at any point, say: **I'm sorry, but unfortunately you are not eligible to participate in this study.** [Explain why they are not eligible if appropriate and indicate reason for ineligibility].

- Not fluent in English
- No diagnosis
- No device to access content
- Age < 18
- Medical condition
- Vision/hearing impairment
- Psychiatric condition
- Moderate/severe
- Low QDRS
- No study partner
- Research study
- Dementia medication change
- Other \_\_\_\_\_

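### The QDRS eligibility rule is written three incompatible ways: the scoring key admits a CDR 1 band that inclusion criterion 2 does not, and the line below the key names only that band

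*Protocol*

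**What the plan says.** **Inclusion criterion 2** (protocol synopsis, Diagnosis and Main Inclusion Criteria) asks for "evidence of MCI, defined as: self-reported quick dementia rating system (QDRS) - derived global clinical dementia rating score of .5". The protocol's Purpose section names the same group; its hypothesis is that "CBT-I is feasible in patients with MCI".

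**The scoring key** (protocol, Appendix B, Quick Dementia Rating System) translates QDRS totals into CDR levels. It labels 2.0 to 6.0 "CDR 0.5 (MCI) -- Eligible" and 6.5 to 12.5 "CDR 1 (mild) -- Eligible". Totals of 0 to 1.5 (normal), 13.0 to 17.5 (moderate) and 18.0 or more (severe) carry no eligible label.

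**The line below the key** reads "If the QDRS score is 6.5 to 12.5, they are eligible", and then sends every other score to an alternative whose symbol did not survive text extraction. The Interviewer Instructions in Appendix B explain that on reaching the script's stop symbol the caller is told "unfortunately you are not eligible to participate in this study". They also list reasons for refusal, including a low QDRS with no cut-off and "Moderate/severe".

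**The SAP** (Procedures, Baseline screening) uses the QDRS-derived CDR to decide eligibility but gives no value. Its Study Aims, Procedures and Follow-up sections describe the population as MCI or mild Alzheimer's disease. Exclusion criterion 1 of the protocol removes people who self-report a physician's diagnosis of Alzheimer's disease or another dementia.

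**The concern.** Criterion 2 and the form used to apply it should admit the same people, and they do not. A person in the CDR 1 band passes the key and fails the criterion. A person in the MCI band meets the criterion and the key, but is not among those whom the line below the key calls eligible.

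Staff who follow the key could pass through screening people whom criterion 2 does not allow. Staff who follow the line below it literally would turn away the MCI group that the Purpose section says is being studied. The line applied decides who is enrolled, what the SAP's eligibility rate measures, and to whom the feasibility results apply. In a pilot whose main product is a statement about feasibility in a named population, that population needs to be defined.

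**Working it through.** No sample size, power or event figure is involved, and the plan states no figure to reproduce. The check applies each rule to the QDRS totals that can occur.

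**Inputs.** The QDRS in Appendix B has ten items, each scored 0, 0.5, 1, 2 or 3. Every half-point total from 0 to 18.0 can be reached, so none of the bands below has gaps. CDR levels are taken from the protocol's own key.

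**Number of totals in a band** = (upper − lower) / 0.5 + 1.

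| Rule | Eligible totals | Count |
|---|---|---|
| Criterion 2 (CDR 0.5, read through the key) | 2.0 to 6.0 | (6.0 − 2.0)/0.5 + 1 = 9 |
| Scoring key (CDR 0.5 or 1) | 2.0 to 12.5 | (12.5 − 2.0)/0.5 + 1 = 22 |
| Line below the key | 6.5 to 12.5 | (12.5 − 6.5)/0.5 + 1 = 13 |

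**Comparisons.**
- Key against criterion 2: 22 − 9 = 13 totals are eligible in the key and not under the criterion; 13/22 = 0.591, or 59%.
- Line below the key against criterion 2: the highest total under criterion 2 is 6.0 and the lowest named in the line is 6.5, so they share none.
- The key is exactly the union of the other two: 9 + 13 = 22.
- If the lost symbol is a stop, all three rules agree only in refusing totals of 0 to 1.5 and of 13.0 or more.

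**Two profiles built from the protocol's items.**
- 0.5 on all ten items: 10 × 0.5 = 5.0, which is CDR 0.5. It passes criterion 2 and the key, and is not named eligible in the line below the key.
- 1 on all ten items: 10 × 1 = 10.0, which is CDR 1. It is eligible in the key and in the line below it, and fails criterion 2.

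**Weight per person.** The synopsis entry "Number of Subjects" is 40. Each person enrolled with a total of 6.5 to 12.5 would be 1/40 = 2.5% of the planned sample.

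**Which reading do the documents favour?** Criterion 2 and the Purpose section point to MCI only. The key and the SAP point to MCI plus mild impairment, and the refusal reason "Moderate/severe" matches the key's CDR 2 and CDR 3 labels. The line below the key fits neither and reads like a drafting slip, since the key directly above it marks the MCI band eligible. Nothing in either document settles the matter.

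**The case against.** The strongest objection is that the three-way conflict rests on damaged text. The symbol after the alternative in the line below the key is lost, and the surviving sentence, that 6.5 to 12.5 is eligible, agrees with the key. This stands in part: reading the symbol as a stop is an inference from the Interviewer Instructions. But the line still names only the CDR 1 band, and the conflict between criterion 2 and the key involves no lost symbol.

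A second objection is that screening is not the last step. Appendix A describes a second appointment to confirm eligibility, and Appendix B says that the final decision follows later. That is why the consequence is put as people who could pass screening. It does not cure the conflict, because neither place says that criterion 2 is applied again.

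Third, nothing shows which line staff would follow, and the list of refusal reasons is a weak guide: it gives an age limit of under 18 in a study of people aged 65 and over. This is fair. It means that the view of the line below the key as a slip is a judgement, and it strengthens the case for stating the rule once. A cut-off for a low QDRS in that list is a minor point, since the key already leaves 0 to 1.5 unmarked.

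Finally, 59% and 2.5% are not effect sizes. That is correct. The first counts points on a scale and the second is one person in 40; the documents give no score distribution from which to estimate how many people are affected.

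**Conclusion.** The concern holds. An inclusion criterion and the form that applies it disagree over a whole severity band, 13 of the 22 totals that the form's key accepts, and the instruction below the key shares no total with the criterion. The first part rests only on the protocol's own mapping of QDRS to CDR. The further claim that the MCI band would be turned away also assumes that the lost symbol is a stop.

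Two limits apply. The SAP's mild Alzheimer's disease wording is in tension with exclusion 1, but the key's CDR 1 band does not by itself contradict that exclusion, because a person can score CDR 1 without a physician's diagnosis. No claim is made about the proportion of eligible participants who consent, a primary feasibility outcome: the SAP places the QDRS interview after consent in one sentence and leaves the order open in another.

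This must be fixed, because until it is, the study population is not defined.

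**What to change.** - Correct the line below the key so that it does not leave out the MCI band, which criterion 2, the Purpose section and the key all include.
- The sponsor chooses one population, either MCI only (QDRS 2.0 to 6.0 on the protocol's key) or MCI plus mild impairment (2.0 to 12.5). State that one range in criterion 2, the key and the line below it.
- Give the low-QDRS refusal reason in the Interviewer Instructions the matching cut-off.
- Bring the SAP's population wording and exclusion 1 into line with the choice, and state the CDR value or values in the SAP's screening section.
- If anyone has already been screened, report which line was applied.

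The cost is wording, including an amendment to criterion 2 if MCI plus mild is chosen. The documents do not say whether screening has begun; if it has, the QDRS totals already recorded must also be checked against the chosen range.
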